4. MAP
 - A. All MAP values obtained 24 hours after the first dose of study drug regardless of administration route.
 - B. MAP values will be obtained at a minimum at the following time points
 - i. Prior to the first dose of study drug or dose escalation: 2 hours (\pm 5 minutes), 1 hour (\pm 5 minutes), and 15 minutes (\pm 5 minutes)
 - ii. If administration route is IV:
 - a. During and following the first dose of study drug or dose escalation: MAP at start of infusion, every 15 minutes (\pm 5 minutes) during infusion, at end of infusion (inclusive of flush) (\pm 5 minutes), at 15 and 30 minutes (\pm 5 minutes) after end of infusion, hourly (\pm 15 minutes) for 4 hours, and once in the remaining 2 hours prior to the next dose.
 - b. For subsequent IV doses, the lowest valid MAP value should be recorded daily while on study drug.
 - iii. If the administration route is enteral:
 - a. During and following the first dose of study drug or dose escalation: MAP at start of enteral administration, then every 15 minutes (\pm 5 minutes) for 90 minutes (1.5 hours), then every 30 minutes (\pm 5 minutes) for 60 minutes (1 hour), then hourly (\pm 15 minutes) for 4 hours, then once in the remaining 2 hours prior to the next dose.
 - b. For subsequent enteral doses, the lowest valid MAP value should be recorded daily while on study drug.
5. Respiratory assessment, daily (Section 8.2.2.3)
6. Laboratory evaluations, at least once every 2 weeks (Section 8.2).
7. Echocardiograms and cardiac catheterization reports, if performed per local standard of care
8. PK sampling (after Day 7 [Section 8.2.2.1])
9. Adverse events (Section 9.3)

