5.2 Participant Exclusion Criteria

An individual who meets any of the following criteria will be excluded from participation in this study:

1. Previous enrollment and dosing in this study, protocol number (NHLBI-2019-SIL), “Safety of Sildenafil in Premature Infants with Severe Bronchopulmonary Dysplasia (BPD)”
2. Previous exposure to sildenafil within 7 days prior to randomization*
3. Previous exposure to vasopressors within 24 hours prior to randomization*
4. Previous exposure to inhaled nitric oxide within 24 hours prior to randomization*
5. Previous exposure to milrinone within 24 hours prior to randomization*
6. Evidence of pulmonary hypertension or moderate/large patent ductus arteriosus (PDA) on the most recent echocardiogram performed within 14 days prior to randomization
7. Known major congenital heart defect requiring medical or surgical intervention in the neonatal period
8. Known allergy to sildenafil
9. Known sickle cell disease

10. Aspartate aminotransferase (AST) > 225 U/L < 72 hours prior to randomization
11. Alanine aminotransferase (ALT) > 150 U/L < 72 hours prior to randomization
12. Any condition that would make the participant, in the opinion of the investigator, unsuitable for the study.

**Participant will be reassessed prior to dosing to reconfirm eligibility criteria.*

Note: Exclusion from participation due to enrollment in other clinical trials, including IND trials, will be left to the judgement of the site principal investigator (PI). Investigator judgement should consider the safety of the participant.

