5.5 Participant Withdrawal or Discontinuation from Study Procedures/Intervention

5.5.1 *Reasons for Participant Withdrawal or Discontinuation from Study Procedures/Intervention*

The participant's parent or guardian may withdraw an infant from participation in the study at any time. Parents or guardians can choose to have infant discontinue study drug and continue to be followed or they can withdraw consent for further participation at any time.

The site investigator may choose to suspend study drug dosing once for up to 48 hours for any reason. If study drug is resumed by the site investigator, the dose and interval of the study drug will be the same as the prior dose. If applicable, subsequent doses will follow the dose escalation or weaning schedule as specified in section 6.1. If study drug is suspended for > 48 hours, the study drug administration will be discontinued and the participant will proceed directly into the safety follow-up period, during which all remaining assessments will be collected. If study drug is suspended for > 48 hours for a documented safety concern, the suspension will not be considered a protocol deviation.

The site investigator will withdraw a participant from receiving further study interventions, including study drug administration, and the participant will enter the 28-day safety-monitoring period if any of the following occur:

- During the course of the study, the participant meets safety-related criteria that would have led to initial exclusion from study participation (i.e., ALT > 150 U/L, AST > 225 U/L, or infant started on vasopressor or inhaled nitric oxide [Section 5.2]).
- Any clinically significant AE (e.g., hypotension) that is deemed by the site investigator to require discontinuation of study drug (see Section 9.5.3 for the definition of hypotension).
- Unmasking of the participant treatment occurs. All unmasking events should be recorded on a protocol deviation form in the EDC system within 24 hours of the unmasking. The decision to unmask will be made in consultation with the medical monitor.

Before discontinuing a participant from the study drug, the site investigator must contact the medical monitor or study PI, except in emergencies. All participants who have study drug suspended will continue to be in the study and complete all remaining study procedures in the safety follow-up period.

5.5.2 Handling of Participant Withdrawals from Study or Participant Discontinuation of Study Intervention

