6 STUDY INTERVENTION

6.1 Study Product Description

In the US, sildenafil, in both IV and for oral suspension, has been approved for use in other populations and for other indications by the FDA¹.

Study dosing and escalation are described in Table 3. Refer to Section 6.1.3 for study drug packaging and labeling.

Table 3 Number of Participants (N) and Dosing Scheme

Cohort ¹	Treatment Group		Sildenafil Dosing ² (mg/kg q 8 hours)		Total (N)
	Placebo (N)	Sildenafil (N)	IV	Enteral	
1	10	30	0.5	1	40
2	10	30	1	2	40
3	10	30	2	4	40

Abbreviations: IV, intravenous; N, number of participants; q, every

1 Participants will be enrolled into cohorts sequentially (i.e., Cohort 1 then Cohort 2 then Cohort 3) based on safety.

2 Route of administration, IV or enteral, is left to investigator discretion.

Dose escalations for each sequential cohort will proceed as summarized in Table 4. DSMB safety review (Section 10) will be required prior to enrolling the next cohort.

Table 4 Dose Escalations for Each Sequential Cohort

	Study Days (Dose Numbers)							
	1-2 (1-6)	3-4 (7-12)	5-6 (13-18)	7-8 (19-24)	9-10 (25-30)	11-12 (31-36)	13-14 (37-42)	15 + (43 +)
Sildenafil Dose (mg/kg)								
Cohort 1								
IV	0.25	0.5	0.5	0.5	0.5	0.5	0.5	0.5
Enteral	0.5	1	1	1	1	1	1	1
Cohort 2								
IV	0.25	0.5	0.75	1	1	1	1	1
Enteral	0.5	1	1.5	2	2	2	2	2
Cohort 3								
IV	0.25	0.5	0.75	1	1.5	1.75	2	2
Enteral	0.5	1	1.5	2	3	3.5	4	4

Abbreviation: IV, intravenous

Dose escalation will occur if the infant is:

1. Receiving exogenous oxygen or respiratory support (nasal cannula or positive pressure from any device); and
2. AST < 225 U/L and ALT < 150 U/L at last check (within 14 days) prior and closest to dose increase.

An infant will meet respiratory criteria for dose escalation only if the infant is receiving exogenous oxygen or respiratory support (nasal cannula or positive pressure from any device) for at least 12 hours before the dose escalation. Infants who do not initially qualify for escalation should be reevaluated daily to ascertain whether they meet these criteria, and escalation must occur within 24 hours of an infant meeting all dose escalation criteria (respiratory and laboratory). If escalation does not occur within this timeframe, then a protocol deviation must be recorded.

Adjusting dose for weight

The actual weight should be reviewed weekly (plus or minus one day, Section 4.2) and the dose of the study drug may be adjusted.

Weaning Period Schedule

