Sildenafil is commonly used at higher doses to treat PH in infants. In clinical practice, it is recommended to wean from these higher doses to prevent rebound effects that may be seen with abrupt discontinuation of sildenafil. Although sildenafil used in this study is for prevention of PH, the target doses in Cohorts 2 and 3 are similar to those used for the treatment of PH.

For Cohorts 2 and 3, weaning of study sildenafil or placebo will begin following the last study dose on Day 28 or if the dose escalates to a dose of ≥ 0.5 mg/kg IV or ≥ 1 mg/kg enteral and the participant is withdrawn from the study. Wean by 25% of last study dose every 2 days until off. Participants should complete weaning after 6 days (Table 5).

Table 5 Weaning Schedule for Study Sildenafil or Placebo in Cohorts 2 and 3

Weaning Days	IV	Enteral
1-2	75% of last study dose	75% of last study dose
3-4	50% of last study dose	50% of last study dose
5-6	25% of last study dose	25% of last study dose
7	Discontinue	Discontinue

Abbreviation: IV, intravenous

If a participant in Cohort 2 or 3, escalates to a dose of ≥ 0.5 mg/kg IV (or ≥ 1 mg/kg enteral) and then is withdrawn from study drug, they will be withdrawn using the weaning schedule outlined above. Deviation from the weaning schedule for documented safety concerns will not result in a protocol deviation.

Weaning is not required for participants in Cohort 1 as the risk of rebound effects is likely minimal for infants receiving low-dose sildenafil.

6.1.1 *Study Placebos*

Intravenous placebo is sterile saline or dextrose 5% and enteral placebo is dextrose 5%.

6.1.2 *Acquisition*

Study drug and placebo will be acquired from the hospital pharmacy. Enteral sildenafil will be supplied to the site pharmacy by Pfizer, Inc. and will be labelled for investigational use. IV sildenafil will be supplied by the site using commercially available products (“off the shelf”).

6.1.3 *Formulation, Packaging, and Labeling*

Intravenous formulation: Only marketed IV formulation for IV administration will be used. This protocol will not specify the brand of product. Each product will be “off the shelf” as provided by the site’s pharmacy. Placebo will be an equal volume of sterile saline or dextrose 5%.

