6.5 Concomitant Medications/Treatments

All drug and/or treatments are permitted while on study. Concomitant medications received within 24 hours prior to start of study drug and those given during the 28-day treatment period will be recorded.

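### Section 5.5.1 does not require masked study drug to stop when open-label sildenafil starts, so an infant can receive both

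*Combined protocol and SAP*

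**What the plan says.** - **Entry (Section 5.2).** One exclusion is "Previous exposure to sildenafil within 7 days prior to randomization".
- **Mandatory stop (Section 5.5.1).** Study drug stops if the infant comes to meet a safety-related entry exclusion. An 'i.e.' list then says which: ALT above 150 U/L, AST above 225 U/L, "or infant started on vasopressor or inhaled nitric oxide".
- **Other routes to a stop (Sections 5.5.1 and 9.5.1).** The investigator may suspend dosing once for up to 48 hours, and a longer suspension becomes discontinuation. The investigator may also withdraw an infant after an adverse event. Unmasking forces withdrawal.
- **Other drugs (Sections 6.5 and 6.5.1).** "All drug and/or treatments are permitted while on study". Sildenafil is among the drugs of special interest to be recorded throughout.
- **Escalation (Section 6.1).** It depends on oxygen or respiratory support and on AST/ALT, and is due within a day of both being satisfied. "If escalation does not occur within this timeframe, then a protocol deviation must be recorded".
- **Blood pressure (Section 4.2).** The enteral schedule opens with "During and following the first dose of study drug or dose escalation: MAP at start of enteral administration" and continues at short intervals. After that, "For subsequent enteral doses, the lowest valid MAP value should be recorded daily while on study drug". The IV rules have the same structure.
- **Wean (Section 6.1, Table 5).** Cohort 2-3 infants who stop after reaching at least 0.5 mg/kg IV or 1 mg/kg enteral get a 6-day wean. Departing from it for a documented safety concern is not a deviation.

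**The concern.** The stop list ends masked dosing when inhaled nitric oxide, another pulmonary vasodilator, is started, but not when a second source of the study drug is started. Open-label use is foreseeable. Section 2.2 says that neonatologists usually treat PH in infants with BPD, and sildenafil is the drug whose growing off-label use it describes. A masked clinician who starts it does not know the infant's current sildenafil dose, and three infants in four are on active drug.

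The main stake is patient safety. Section 6.1 notes that "the target doses in Cohorts 2 and 3 are similar to those used for the treatment of PH", so in those cohorts the open-label dose would be added to a dose already in the treatment range. Hypotension is the primary outcome, and the single related event in the phase 1 study was hypotension after an infusion that ran faster than expected. The lesser stake is attribution: hypotension after an open-label start is counted under the assigned arm, and Section 12.4 describes no split at that point.

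**Working it through.** **The plan's own figures.** The documents give no number for combined exposure. The sample-size figures in Section 12.2 reproduce: 1 - 0.95^30 = 0.785 (stated 78%) and 1 - 0.95^90 = 0.990 (stated 99%). This point leaves them unchanged.

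**Is a stop required?** Section 5.2 has four time-limited drug exclusions: sildenafil, vasopressors, inhaled nitric oxide and milrinone. The 5.5.1 list carries over only vasopressors and inhaled nitric oxide. Section 6.5 bars nothing, 6.5.1 only records, and the escalation criteria in 6.1 do not mention open-label sildenafil. No provision requires masked drug to be stopped, held or capped.

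**How long does the escalation rule apply?** From Table 4, target dose is reached on Day 3 (Cohort 1), Day 7 (Cohort 2) and Day 13 (Cohort 3) if nothing is delayed. Before that day 6.1 calls for escalation; afterwards the masked dose continues at target.

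**Combined daily dose (illustration).** Inputs are the enteral targets in Table 3, given three times a day, and the two case-series ranges in Section 2.2 (1.5-8 and 1-7.3 mg/kg/day, together 1-8). Using 1-8 as the open-label dose is an assumption.

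| Cohort | Masked enteral target (mg/kg/day) | Plus 1 to 8 (mg/kg/day) |
|---|---|---|
| 1 | 1 x 3 = 3 | 4-11 |
| 2 | 2 x 3 = 6 | 7-14 |
| 3 | 4 x 3 = 12 | 13-20 |

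The upper ends assume the top of a range reported without any study drug, so they are worst case.

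**Size of the step.** Cohort 3 enteral steps in Table 4 are 0.5, 0.5, 0.5, 1, 0.5 and 0.5 mg/kg per dose. Times three, that is five steps of 1.5 and one of 3 mg/kg/day. An open-label dose exceeds the largest planned step only if it is above 3 mg/kg/day. A dose of 1 is smaller than every planned step.

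**Wean after a stop at target.** At 75, 50 and 25%, Cohort 3 gets 9, 6 and 3 mg/kg/day and Cohort 2 gets 4.5, 3 and 1.5, two days each, unless the safety-concern provision is used.

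**Attribution.** One event moves the pooled placebo rate (3 x 10 = 30 infants) or one dose-cohort rate (30) by 1/30 = 3.3 points, and the pooled sildenafil rate by 1/90 = 1.1 points.

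**PK sampling (Section 8.2.2.1).** It opens after 7 days at target: about Day 3 + 7 = 10, 7 + 7 = 14 and 13 + 7 = 20 in Cohorts 1, 2 and 3.

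**The case against.** The opening words of the 5.5.1 bullet refer generally to safety-related entry exclusions, and a careful site could read them to include sildenafil. The 'i.e.' list points the other way, so sites may differ. An investigator who is worried can suspend dosing for any reason, withdraw the infant at any time, and depart from the wean for a documented safety concern. These options are real, but all are discretionary. A short suspension also ends with dosing resumed on the escalation schedule.

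Several stronger readings are tempting, and the documents do not support them:

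- *That 6.1 forces escalation throughout.* It does so only before target dose. Recent echocardiographic PH is excluded at entry, and Section 2.2 says most BPD-related PH comes later, which narrows the overlap further.
- *That an open-label start always exceeds any planned step.* This is true only above 3 mg/kg/day enteral. The cited series report dose ranges, not starting doses.
- *That the wean necessarily adds to open-label drug.* The safety-concern provision in 6.1 already allows a departure.
- *That a known number of infants would be affected.* Section 2.2 gives about 20% for PH in severe BPD, without a time window, so 0.20 x 90 = 18. Any count of infants receiving both drugs needs a share started on open-label sildenafil during dosing. Assuming 10-50% gives about 2-9, but that share has no source.
- *That hypotension would go unseen.* The MAP schedule is a minimum, and the endpoint is hypotension that the treating physician judges to need intervention, reported within 24 hours. Capturing it does not depend on the intensive schedule.
- *That the sildenafil-placebo comparison is biased in a known direction.* Open-label use can occur in both arms. Events are assessed for relatedness, and the separate SAP cited in Section 12.4 was not available.

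**Conclusion.** The gap stands. As written, the protocol permits masked study drug and open-label sildenafil together and requires a stop only if something else intervenes. Before target dose, the escalation rule works against caution; after it, masked dosing simply continues. The intensive MAP schedule is tied to study-drug events, so an open-label start does not trigger it.

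The frequency is unknown. The combined totals of 4-11, 7-14 and 13-20 mg/kg/day rest on enteral dosing at target and an assumed open-label dose of 1-8 mg/kg/day. The conclusion that overlap is permitted rests on the text alone. This is an inexpensive safety clarification that should be made. It does not invalidate the design or the primary summary, and the effect on attribution is minor and of uncertain direction.

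**What to change.** 1. **Section 5.5.1:** add 'or infant started on open-label sildenafil' to the stop list. Keep the 28-day safety follow-up and the as-assigned hypotension summary as primary.
2. **Section 6.1, wean, Cohorts 2-3:** state that while open-label sildenafil is running, the study-drug wean is decided case by case with the medical monitor or study PI, whom 5.5.1 already requires the site to contact except in emergencies. State also that omitting or shortening the wean then counts as a documented safety concern. A flat no-wean rule would be wrong. An infant at 12 mg/kg/day moved to a low open-label dose would drop abruptly, and the wean exists to prevent rebound.
3. **Optional:** if the separate SAP does not already have it, add a descriptive table of hypotension before and after open-label start, by arm. It would also cover open-label use that begins after study drug has ended, which the stop rule cannot reach. Check that the eCRF holds the start date and time.

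**Cost.** One clause, a short addition to the wean text and perhaps one table. Some infants, number unknown, will stop study drug earlier. PK samples are lost when the stop precedes sampling, so Cohort 3 is most exposed. A stop before 7 days of drug takes the infant out of the PP population, though not the Safety population, and may allow replacement under Section 5.4.1. The post-treatment echocardiogram comes earlier for these infants.

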5.6 Premature Termination or Suspension of Study

This study may be terminated at any time by the IND sponsor after consultation with FDA, NIH, and/or the Data Safety Monitoring Board DSMB. If the study is terminated, notification to FDA and US investigators will be made in accordance with 21 CFR 312.56(d).

If the study is discontinued, enrolled participants will continue to be followed for safety assessments through 28 days after last dose of study drug. All AEs must be followed through resolution. If the study is discontinued, regulatory authorities, IRBs and participant parents/guardians will be notified as required by regulation (e.g., U.S. 21 CFR 312.56).

6 STUDY INTERVENTION

6.1 Study Product Description

In the US, sildenafil, in both IV and for oral suspension, has been approved for use in other populations and for other indications by the FDA¹.

Study dosing and escalation are described in Table 3. Refer to Section 6.1.3 for study drug packaging and labeling.

Table 3 Number of Participants (N) and Dosing Scheme

Cohort ¹	Treatment Group		Sildenafil Dosing ² (mg/kg q 8 hours)		Total (N)
	Placebo (N)	Sildenafil (N)	IV	Enteral	
1	10	30	0.5	1	40
2	10	30	1	2	40
3	10	30	2	4	40

Abbreviations: IV, intravenous; N, number of participants; q, every

1 Participants will be enrolled into cohorts sequentially (i.e., Cohort 1 then Cohort 2 then Cohort 3) based on safety.

2 Route of administration, IV or enteral, is left to investigator discretion.

Dose escalations for each sequential cohort will proceed as summarized in Table 4. DSMB safety review (Section 10) will be required prior to enrolling the next cohort.

Table 4 Dose Escalations for Each Sequential Cohort

	Study Days (Dose Numbers)							
	1-2 (1-6)	3-4 (7-12)	5-6 (13-18)	7-8 (19-24)	9-10 (25-30)	11-12 (31-36)	13-14 (37-42)	15 + (43 +)
Sildenafil Dose (mg/kg)								
Cohort 1								
IV	0.25	0.5	0.5	0.5	0.5	0.5	0.5	0.5
Enteral	0.5	1	1	1	1	1	1	1
Cohort 2								
IV	0.25	0.5	0.75	1	1	1	1	1
Enteral	0.5	1	1.5	2	2	2	2	2
Cohort 3								
IV	0.25	0.5	0.75	1	1.5	1.75	2	2
Enteral	0.5	1	1.5	2	3	3.5	4	4

Abbreviation: IV, intravenous

Dose escalation will occur if the infant is:

1. Receiving exogenous oxygen or respiratory support (nasal cannula or positive pressure from any device); and
2. AST < 225 U/L and ALT < 150 U/L at last check (within 14 days) prior and closest to dose increase.

An infant will meet respiratory criteria for dose escalation only if the infant is receiving exogenous oxygen or respiratory support (nasal cannula or positive pressure from any device) for at least 12 hours before the dose escalation. Infants who do not initially qualify for escalation should be reevaluated daily to ascertain whether they meet these criteria, and escalation must occur within 24 hours of an infant meeting all dose escalation criteria (respiratory and laboratory). If escalation does not occur within this timeframe, then a protocol deviation must be recorded.

Adjusting dose for weight

The actual weight should be reviewed weekly (plus or minus one day, Section 4.2) and the dose of the study drug may be adjusted.

Weaning Period Schedule

Sildenafil is commonly used at higher doses to treat PH in infants. In clinical practice, it is recommended to wean from these higher doses to prevent rebound effects that may be seen with abrupt discontinuation of sildenafil. Although sildenafil used in this study is for prevention of PH, the target doses in Cohorts 2 and 3 are similar to those used for the treatment of PH.

For Cohorts 2 and 3, weaning of study sildenafil or placebo will begin following the last study dose on Day 28 or if the dose escalates to a dose of ≥ 0.5 mg/kg IV or ≥ 1 mg/kg enteral and the participant is withdrawn from the study. Wean by 25% of last study dose every 2 days until off. Participants should complete weaning after 6 days (Table 5).

Table 5 Weaning Schedule for Study Sildenafil or Placebo in Cohorts 2 and 3

Weaning Days	IV	Enteral
1-2	75% of last study dose	75% of last study dose
3-4	50% of last study dose	50% of last study dose
5-6	25% of last study dose	25% of last study dose
7	Discontinue	Discontinue

Abbreviation: IV, intravenous

If a participant in Cohort 2 or 3, escalates to a dose of ≥ 0.5 mg/kg IV (or ≥ 1 mg/kg enteral) and then is withdrawn from study drug, they will be withdrawn using the weaning schedule outlined above. Deviation from the weaning schedule for documented safety concerns will not result in a protocol deviation.

Weaning is not required for participants in Cohort 1 as the risk of rebound effects is likely minimal for infants receiving low-dose sildenafil.

6.1.1 *Study Placebos*

Intravenous placebo is sterile saline or dextrose 5% and enteral placebo is dextrose 5%.

6.1.2 *Acquisition*

Study drug and placebo will be acquired from the hospital pharmacy. Enteral sildenafil will be supplied to the site pharmacy by Pfizer, Inc. and will be labelled for investigational use. IV sildenafil will be supplied by the site using commercially available products (“off the shelf”).

6.1.3 *Formulation, Packaging, and Labeling*

Intravenous formulation: Only marketed IV formulation for IV administration will be used. This protocol will not specify the brand of product. Each product will be “off the shelf” as provided by the site’s pharmacy. Placebo will be an equal volume of sterile saline or dextrose 5%.

Enteral formulation: The enteral formulation of sildenafil (Revatio[®]) will be provided for the study by Pfizer, Inc. Study drug will be shipped to each site pharmacy by the drug distribution vendor, Almac. Placebo will be an equal volume of dextrose 5%.

Any requisite clinical trial materials will be provided with labeling in accordance with applicable regulatory requirements. Information regarding dosage, preparation and administration of study drug is detailed in Section 6.2 below.

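### Table 4 sets the dose by both study day and dose number; after the permitted 48-hour pause the two give different doses in Cohorts 2 and 3, and the level due after late qualification is not stated

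*Combined protocol and SAP*

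**What the plan says.** Section 6.1 states: "Dose escalations for each sequential cohort will proceed as summarized in Table 4". Each Table 4 column is headed by a range of study days with a range of dose numbers in brackets, for example Days 7-8 with doses 19-24. No column, footnote or sentence refers to time spent at the current level.

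An infant steps up only if on oxygen or respiratory support for at least the preceding 12 hours and with AST and ALT under the limits at the last check. For the rest, "Infants who do not initially qualify for escalation should be reevaluated daily to ascertain whether they meet these criteria". Once all criteria are met the step is due within 24 hours, and missing that window is a deviation. The level to step to is not named.

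Section 5.5.1 adds: "The site investigator may choose to suspend study drug dosing once for up to 48 hours for any reason". On resumption "the dose and interval of the study drug will be the same as the prior dose", and after that, where applicable, "subsequent doses will follow the dose escalation or weaning schedule as specified in section 6.1". It does not say whether the missed doses count towards the dose number. Section 4.2 (blood pressure monitoring) and Section 6.3 (weight adjustment) do not settle the matter.

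**The concern.** A dosing table with two indices is safe only if the indices cannot separate. Here the protocol itself allows an event, the pause, that separates them by up to one full column. The same infant can then be due two different doses under the same table, and one of the two passes over a titration level. For late qualification the problem is silence: there is a deadline for stepping up but no stated destination.

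The primary outcome is hypotension, summarized by dose cohort, and the trial reaches its target doses by stepwise titration. The two readings would give a paused infant different doses during titration and different days of arrival at the target dose.

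**Working it through.** **Inputs.** Dosing is every 8 hours, so 3 doses per day (Table 3). Levels and column headers are from Table 4. The pause is one, up to 48 hours, so up to 48/8 = 6 doses (Section 5.5.1). Assumptions: three doses in each study day, dose number counts doses actually given, and the infant meets the escalation criteria after the pause.

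**Reproducing the table.** Without interruption, Day d carries doses 3(d-1)+1 to 3d. Days 9-10 give 25 to 30 and Days 13-14 give 37 to 42, as printed. All eight columns match, so the keys agree for uninterrupted dosing.

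**On-schedule steps, Cohort 3 IV.** Levels are 0.25, 0.5, 0.75, 1, 1.5, 1.75 and 2 mg/kg. Successive ratios are 2.0, 1.5, 1.33, 1.5, 1.17 and 1.14.

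**After a 48-hour pause.** If the pause follows the end of Day d, dosing resumes on Day d+3 with dose 3d+1, fixed at the prior dose by Section 5.5.1. The first dose governed by Table 4 again is 3d+2. Cohort 3 IV (mg/kg):

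| Pause after Day | Prior dose | Next dose no., day | By study day (ratio to prior) | By dose number (ratio to prior) | Level skipped by study-day key |
|---|---|---|---|---|---|
| 2 | 0.25 | 8, Day 5 | 0.75 (3.0) | 0.5 (2.0) | 0.5 |
| 4 | 0.5 | 14, Day 7 | 1 (2.0) | 0.75 (1.5) | 0.75 |
| 6 | 0.75 | 20, Day 9 | 1.5 (2.0) | 1 (1.33) | 1 |
| 8 | 1 | 26, Day 11 | 1.75 (1.75) | 1.5 (1.5) | 1.5 |
| 10 | 1.5 | 32, Day 13 | 2 (1.33) | 1.75 (1.17) | 1.75 |
| 12 | 1.75 | 38, Day 15 | 2 (1.14) | 2 (1.14) | none |

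Enteral doses are twice the IV doses in every cell, so the ratios are the same. The first two rows also hold in Cohort 2. Pauses after odd-numbered days separate the keys without skipping a level. For example, after Day 5 the study-day key gives 1 and the dose-number key stays at 0.75. The dose-number key never skips a level after a pause.

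**Extent.** A six-dose pause shifts the keys by exactly one column. They therefore disagree until dose numbers reach the last level's column: through dose 36 in Cohort 3, 18 in Cohort 2 and 6 in Cohort 1.
- Cohort 3: pauses after any of Days 1-11. Pausing after Day 6 affects doses 19-36, that is 18 doses, or 17 after setting aside the resumed dose that Section 5.5.1 fixes.
- Cohort 2: pauses after any of Days 1-5.
- Cohort 1: only a pause within Days 1-2. There is a single step, so no level can be skipped.

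**Late qualification.** No doses are missed, so the keys agree; the open question is the level. In Cohorts 2 and 3, an infant still at 0.25 mg/kg IV who first qualifies on Day 5 (dose 13) is in the 0.75 column, while the next unused level is 0.5. On Day 7 (dose 19) the column reads 1 and the next unused level is still 0.5.

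**The case against.** The case for leaving the text alone has substance. The resumed dose equals the prior dose, so nothing jumps at restart. Only one pause is allowed. Blood pressure is monitored closely around escalations (Section 4.2). Every dose is recorded with time, amount and route; PK samples follow 7 days at the target dose (Section 8.2.2.1); and the effectiveness model uses maximum and total dose (Section 12.4). Most analyses can therefore use the doses actually given. All of this stands, and it limits the consequences, but it does not say which dose is due.

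One might also infer that elapsed days govern, because the 34-day maximum in the Protocol Summary is 28 + 6 weaning days with no allowance for a pause. That figure concerns duration, not the level after a pause, and the protocol never makes the link. If dose numbers were meant to run on through a pause, the keys would agree again, but that is not stated either.

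Several stronger readings are tempting and are not supported:
- **The table prescribes 6- or 8-fold steps after a delay.** These ratios (1.5/0.25 on Day 9 and 2/0.25 on Day 13, Cohort 3) need an infant held at the first level for a week or more and a literal column reading. Section 6.1 names no target level. Transaminases above the limits lead to withdrawal under Section 5.5.1, not a held step. A respiratory hold needs an infant enrolled on ventilation or CPAP to come off support and later return to it.
- **Daily steps would comply.** The 24-hour rule addresses infants who did not qualify at first, and Table 4 shows two days at each level before target.
- **A late first dose on Day 1 also splits the keys.** That requires midnight-to-midnight dosing days, which are not defined; Section 8.2.2.1 equates 7 days of study drug with 168 hours. The calendar-date remark under Table 6 concerns baseline procedures.
- **Sites will dose identical infants differently.** The protocol refers dosing and administration detail to the Manual of Procedures, which is not available here, so divergent practice is possible but not shown.

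**Conclusion.** The pause conflict holds on the text. After a full 48-hour pause during titration in Cohorts 2 and 3, the two keys give different doses and nothing in the protocol chooses between them. In the Day 6 example the choice is 1.5 or 1.0 mg/kg IV after 0.75. Across possible pause times in Cohort 3, the study-day key's first step after the resumed dose reaches at most 3-fold (pause after Day 2), against a largest on-schedule step of 2-fold.

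The late-qualification point also holds, as a gap: the destination level is unstated, and a literal column reading would skip levels in Cohorts 2 and 3. It is not an express instruction to skip, and the keys do not conflict there.

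The result rests on three doses per study day and on dose numbers counting doses given. The number of infants affected cannot be computed, since the protocol gives no frequency for pauses or delays; long delays are probably uncommon. The point merits correction because the ambiguity concerns dose in a trial whose primary outcome is hypotension.

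**What to change.** Reconcile Table 4, the daily re-evaluation paragraph in Section 6.1 and Section 5.5.1. State one key that yields a single dose after a pause, and label the other as applying only if dosing is uninterrupted. Say whether missed doses count. For late qualification, state which level follows and when the step after it is due. Which key, level and interval apply is for the sponsor to decide.

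The cost is a short amendment (a table header and about two sentences), with matching pharmacy and EDC instructions.
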